4.4 Eligibility/screening of subjects

If potential subjects will be asked eligibility questions before obtaining informed consent, describe the process. Add the script documents and a list of the eligibility questions that will be used to your study in CATS IRB (<http://irb.psu.edu>) on the "Consent Forms and Recruitment Materials" page.

StudyFinder: If you intend to use StudyFinder (<http://studyfinder.psu.edu>) for recruitment purposes, any scripts (phone, email, or other) used when contacting StudyFinder participants as well as any eligibility screening questions must be added to your study in CATS IRB (<http://irb.psu.edu>) on the "Consent Forms and Recruitment Materials" page.

There are no additional screening questions for providers.

We will not be asking subjects additional eligibility questions. As they are recruited by providers, we are using the eligibility criteria of the parenting program (Incredible Years or PAT or SC) as the only screener.

In other words, if they are enrolled or enrolling in either of these programs, and meet the other criteria (English-speaking, over 18, and a parent/caregiver to a child under 13) then there are no additional screening items. These eligibility criteria (and whether a parent meets them or not) will be known by the providers prior to approaching a family. If a parent receiving PAT or SC is ineligible, they will not be presented with an opportunity to participate. Incredible Years providers will conduct sessions with eligible parents for the research and separate sessions for ineligible parents.

5.0 Consent Process and Documentation

Refer to “SOP: Informed Consent Process for Research (HRP-090)”, for information about the process of obtaining informed consent from subjects. HRP-090 can be accessed by clicking the Library link in CATS IRB (<http://irb.psu.edu>).

5.1 Consent Process

5.1.1 Obtaining Informed Consent

5.1.1.1 Timing and Location of Consent

Describe where and when the consent process will take place.

Providers will consent to be audio recorded for fidelity purposes at the time of SPSHK training. These trainings will occur at the agency site.

Consent will occur at the time and location of recruitment (IY: the community center or agency where the group occurs, PAT or SafeCare: the subject’s home). This is prior to any delivery of intervention (i.e., parent-education program) content.

5.1.1.2 Coercion or Undue Influence during Consent

Describe the steps that will be taken to minimize the possibility of coercion or undue influence in the consent process.

The researcher will stress that participation is optional to all participants (providers and parents). Potential provider-subjects will be reminded that they will receive the SPSHK training regardless of their decision to participate as a research subject (i.e., in the fidelity study). Additionally, we will make it clear that any site-level incentives provided to agencies are not dependent upon the number of providers that enroll as research subjects. Potential parent participants are also reminded that they may decline to participate in the research (i.e., surveys), but still participate in the parenting program.

5.1.2 Waiver or alteration of the informed consent requirement

If you are requesting a waiver or alteration of consent (consent will not be obtained, required information will not be disclosed, or the research involves deception), describe the rationale for the request in this section. If the alteration is because of deception or incomplete disclosure, explain whether and how subjects will be debriefed. Add any debriefing materials or document(s) to your study in CATS IRB (<http://irb.psu.edu>) on the “Supporting Documents” page. NOTE: Review the “CHECKLIST: Waiver or Alteration of Consent Process (HRP-410)” to ensure you have provided sufficient information for the IRB to make these determinations. HRP-410 can be accessed by clicking the Library link in CATS IRB (<http://irb.psu.edu>).

Not applicable

5.2 Consent Documentation

5.2.1 Written Documentation of Consent

Refer to “SOP: Written Documentation of Consent (HRP-091)” for information about the process to document the informed consent process in writing. HRP-091 can be accessed by clicking the Library link in CATS IRB (<http://irb.psu.edu>).

If you will document consent in writing, describe how consent of the subject will be documented in writing. Add the consent document(s) to your study in CATS IRB (<http://irb.psu.edu>) on the “Consent Forms and Recruitment Materials” page. Links to Penn State’s consent templates are available in the same location where they are uploaded and their use is required.

Written consent will be obtained for all participants (program subjects and provider-subjects).

5.2.2 Waiver of Documentation of Consent (Implied consent, Verbal consent, etc.)

If you will obtain consent (verbal or implied), but not document consent in writing, describe how consent will be obtained. Add the consent script(s) and/or information sheet(s) to your study in CATS IRB (<http://irb.psu.edu>) on the “Consent Forms and Recruitment Materials” page. Links to Penn State’s consent templates are available in the same location where they are uploaded and their use is required. Review “CHECKLIST: Waiver of Written Documentation of Consent (HRP-411)” to ensure that you have provided sufficient information. HRP-411 can be accessed by clicking the Library link in CATS IRB (<http://irb.psu.edu>).

If your research presents no more than minimal risk of harm to subjects and involves no procedures for which written documentation of consent is normally required outside of the research context, the IRB will generally waive the requirement to obtain written documentation of consent.

Not applicable

5.3 Consent – Other Considerations

5.3.1 Non-English Speaking Subjects

Indicate what language(s) other than English are understood by prospective subjects or representatives.

If subjects who do not speak English will be enrolled, describe the process to ensure that the oral and written information provided to those subjects will be in that language. Indicate the language that will be used by those obtaining consent.

Indicate whether the consent process will be documented in writing with the long form of the consent documentation or with the short form of the consent documentation. Review the “SOP: Written Documentation of Consent (HRP-091)” and the “Investigator Manual (HRP-103)” to ensure that you have provided sufficient information. HRP-091 and HRP-103 can be accessed by clicking the Library link in CATS IRB (<http://irb.psu.edu>).

Due to current limitations in program materials available, only English-speaking subjects will be recruited.

5.3.2 Cognitively Impaired Adults

Refer to “CHECKLIST: Cognitively Impaired Adults (HRP-417)” for information about research involving cognitively impaired adults as subjects. HRP-417 can be accessed by clicking the Library link in CATS IRB (<http://irb.psu.edu>).

5.3.2.1 Capability of Providing Consent

Describe the process to determine whether an individual is capable of consent.

Adults with cognitive disabilities have unique parenting circumstances that, though important, are beyond the scope of the proposed research.

5.3.2.2 Adults Unable To Consent

Describe whether and how informed consent will be obtained from the legally authorized representative. Describe who will be allowed to provide informed consent. Describe the process used to determine these individual’s authority to consent to research.

For research conducted in the state, review “SOP: Legally Authorized Representatives, Children and Guardians (HRP-013)” to be aware of which individuals in the state meet the definition of “legally authorized representative”. HRP-013 can be accessed by clicking the Library link in CATS IRB (<http://irb.psu.edu>).

For research conducted outside of the state, provide information that describes which individuals are authorized under applicable law to consent on behalf of a prospective subject to their participation in the procedure(s) involved in this research. One method of obtaining this information is to have a legal counsel or authority review your protocol along with the definition of “children” in “SOP: Legally Authorized Representatives, Children, and Guardians (HRP-013).” HRP-013 can be accessed by clicking the Library link in CATS IRB (<http://irb.psu.edu>).

Not applicable: Adults with cognitive disabilities have unique parenting circumstances that, though important, are beyond the scope of the proposed research.

5.3.2.3 Assent of Adults Unable to Consent

Describe the process for assent of the subjects. Indicate whether assent will be required of all, some or none of the subjects. If some, indicate which subjects will be required to assent and which will not.

If assent will not be obtained from some or all subjects, provide an explanation of why not.

Describe whether assent of the subjects will be documented and the process to document assent. The IRB allows the person obtaining assent to document assent on the consent document and does not routinely require assent documents and does not routinely require subjects to sign assent documents.

Not applicable

5.3.3 Subjects who are not yet adults (infants, children, teenagers)

5.3.3.1 Parental Permission

Describe whether and how parental permission will be obtained. If permission will be obtained from individuals other than parents, describe who will be allowed to provide permission. Describe the process used to determine these individual's authority to consent to each child's general medical care.

For research conducted in the state, review "SOP: Legally Authorized Representatives, Children and Guardians (HRP-013)" to be aware of which individuals in the state meet the definition of "children". HRP-013 can be accessed by clicking the Library link in CATS IRB (<http://irb.psu.edu>).

For research conducted outside of the state, provide information that describes which persons have not attained the legal age for consent to treatments or procedures involved in the research, under the applicable law of the jurisdiction in which research will be conducted. One method of obtaining this information is to have a legal counsel or authority review your protocol along with the definition of "children" in "SOP: Legally Authorized Representatives, Children, and Guardians (HRP-013)." HRP-013 can be accessed by clicking the Library link in CATS IRB (<http://irb.psu.edu>).

Not applicable

5.3.3.2 Assent of subjects who are not yet adults

Indicate whether assent will be obtained from all, some, or none of the children. If assent will be obtained from some children, indicate which children will be required to assent. When assent of children is obtained describe whether and how it will be documented.

Not applicable

6.0 HIPAA Research Authorization and/or Waiver or Alteration of Authorization

This section is about the access, use or disclosure of Protected Health Information (PHI). PHI is individually identifiable health information (i.e., health information containing one or more 18 identifiers) that is transmitted or maintained in any form or medium by a Covered Entity or its Business Associate. A Covered Entity is a health plan, a health care clearinghouse or health care provider who transmits health information in electronic form. See the "Investigator Manual (HRP-103)" for a list of the 18 identifiers. HRP-103 can be accessed by clicking the Library link in CATS IRB (<http://irb.psu.edu>).

If requesting a waiver/alteration of HIPAA authorization, complete sections 6.2 and 6.3 in addition to section 6.1. The Privacy Rule permits waivers (or alterations) of authorization if the research meets certain conditions. Include only information that will be accessed with the waiver/alteration.

6.1 Authorization and/or Waiver or Alteration of Authorization for the Uses and Disclosures of PHI

Check all that apply:

- Not applicable, no identifiable protected health information (PHI) is accessed, used or disclosed in this study.** [Mark all parts of sections 6.2 and 6.3 as not applicable]

- Authorization will be obtained and documented as part of the consent process.** *[If this is the only box checked, mark sections 6.2 and 6.3 as not applicable]*
- Partial waiver is requested for recruitment purposes only (Check this box if patients' medical records will be accessed to determine eligibility before consent/authorization has been obtained).** *[Complete all parts of sections 6.2 and 6.3]*
- Full waiver is requested for entire research study (e.g., medical record review studies).** *[Complete all parts of sections 6.2 and 6.3]*
- Alteration is requested to waive requirement for written documentation of authorization (verbal authorization will be obtained).** *[Complete all parts of sections 6.2 and 6.3]*

6.2 Waiver or Alteration of Authorization for the Uses and Disclosures of PHI

6.2.1 Access, use or disclosure of PHI representing no more than a minimal risk to the privacy of the individual

6.2.1.1 Plan to protect PHI from improper use or disclosure

Include the following statement as written – DO NOT ALTER OR DELETE unless this section is not applicable because the research does not involve a waiver of authorization. If the section is not applicable, remove the statement and indicate as not applicable.

Not applicable

6.2.1.2 Plan to destroy identifiers or a justification for retaining identifiers

Describe the plan to destroy the identifiers at the earliest opportunity consistent with the conduct of the research. Include when and how identifiers will be destroyed. If identifiers will be retained, provide the legal, health or research justification for retaining the identifiers.

Not applicable

6.2.2 Explanation for why the research could not practicably be conducted without access to and use of PHI

Provide an explanation for why the research could not practicably be conducted without access to and use of PHI.

Not applicable

6.2.3 Explanation for why the research could not practicably be conducted without the waiver or alteration of authorization

Provide an explanation for why the research could not practicably be conducted without the waiver or alteration of authorization.

Not applicable

6.3 Waiver or alteration of authorization statements of agreement

By submitting this study for review with a waiver of authorization, you agree to the following statement – DO NOT ALTER OR DELETE unless this section is not applicable because the research does not involve a

waiver or alteration of authorization. If the section is not applicable, remove the statement and indicate as not applicable.

Not applicable

7.0 Study Design and Procedures

7.1 Study Design

Describe and explain the study design.

This research will utilize a randomized controlled trial (RCT) design. As this research includes three parenting programs, Incredible Years, PAT, and SafeCare, three RCTs will be conducted simultaneously. Randomization will occur at the site level to reduce the potential for contamination; as such, recruited parents will not be informed of the randomization process. When sites agree to participate (i.e., be randomized) they agree to implement the evidence-based parenting program plus the added module as they would typically implement the parenting program. Although the module is not evidence-based, they are agreeing to deliver as if it were standard procedure.

This section describes the design and procedures for the three RCTs: (1) *Incredible Years RCT*; (2) *Parents as Teachers RCT* and (3) *SafeCare RCT*. However, there are commonalities between the three trials:

- There will be two groups of providers— one assigned to deliver the parenting program and one assigned to deliver the parenting program plus additional SPSHK module at the end of the last session (described below), in support of the research question.
- Parents in the control group will complete assessments at four time points: pre-parenting intervention, post-parenting intervention, one-week post parenting, and one month post-intervention.
- Parents in the experimental group will complete assessments at four time points: pre-parenting intervention, post-parenting intervention, post-module, and one month post-intervention.
- For the experimental group, fidelity monitoring procedures will also occur in sessions for each enrolled provider-subjects. Parents and provider-subjects of these sessions will each complete a fidelity assessment instrument. With the parent’s permission, the provider will audio record two experimental sessions.

Different measures will be asked at specific assessment periods:

Measure Name (file name in supporting documents attachments)	Construct	Timing of Delivery (by Protocol Section description paragraph)
Alabama Parenting Questionnaire (APQ; ‘Measure_APQ.docx’)	Parenting behaviors and responding to child’s externalizing behaviors: subscales of Parental Involvement, Positive Parenting, Inconsistent Discipline Practices	7.2.1, 7.2.3, 7.2.5, 7.2.6
Alcohol Use Disorders Identification Test (AUDIT; ‘Measure_AUDIT.docx’)	Assesses alcohol consumption, drinking behaviors, and alcohol-related problems.	7.2.1
Center for Epidemiologic Studies Depression Scale (CES-D; ‘Measure_CESD.docx’)	Screening test for depressive symptoms and depressive disorder	7.2.1

Drug Abuse Screening Test (DAST; 'Measure_DAST.docx')	Assesses drug use, not including alcohol or tobacco use, in the past 12 months	7.2.1
Demographics ('Measure_Demographics.docx')		7.2.1
Interpersonal Support Evaluation List (ISEL; 'Measure_ISEL-SF.docx')	Perceptions of social support (Appraisal, Belonging, Tangible)	7.2.1
Parent Satisfaction Survey ('Measure_ParentSatisfactionSurvey.docx')	Satisfaction with added module	7.2.5
Module Assessment ('Measure_ParentAssessmentTool.docx')	Assessment of attitudes, knowledge, behavior of CSA prevention	7.2.1, 7.2.3, 7.2.5, 7.2.6
Readiness, Efficacy, Attributions, Defensiveness, and Importance Scale (READI-SF; 'Measure_READI-SF.docx')	Assessment of parent's readiness to engage in services	7.2.1
SPSHK Parent Fidelity Monitoring (experimental group only; 'SPSHK Parent Fidelity Monitoring_v3.docx')	Parent assessment of session fidelity	7.2.4
SPSHK Provider Fidelity Monitoring measure (provider-subjects only, of experimental sessions)	Provider self-report assessment of fidelity	7.2.4
SPSHK Researcher Fidelity Monitoring (of audio recorded session; 'SPSHK Researcher Fidelity Monitoring_v2.docx')	Researcher assessment of session fidelity	7.2.4

Time points and measures used

Assessment Time Point	(Protocol Section)	Measures
Pre-parenting Intervention Assessment	(7.2.1)	APQ AUDIT CES-D DAST Demographics ISEL-SF Module Assessment READI-SF
Post-parenting Intervention Assessment	(7.2.3)	APQ Module Assessment
One-week post parenting (control group) or Post-parenting and SPSHK Module Assessment (experimental group)	(7.2.4)	APQ Module Assessment Parent Satisfaction Survey SPSHK Parent Fidelity Monitoring (experimental group only) SPSHK Researcher Fidelity Monitoring (experimental group only) SPSHK Provider Fidelity Monitoring (experimental group only)
One-month Follow-up Assessment	(7.2.5)	APQ Module Assessment

7.2 Study Procedures

Provide a description of all research procedures being performed and when they are being performed (broken out by visit, if applicable), including procedures being performed to monitor subjects for safety or minimize risks. Include any long-term follow-up procedures and data collection, if applicable.

Describe where or how you will be obtaining information about subjects (e.g., medical records, school records, surveys, interview questions, focus group topics, audio or video recordings, data collection forms, and collection of specimens through invasive or non-invasive procedures to include the amount to be collected and how often). Add any data collection instruments that will be seen by subjects to your study in CATS IRB (<http://irb.psu.edu>) in the “Supporting Documents” page.

7.2.1 Pre-parenting Intervention Assessment

Provide a description as defined above and format accordingly.

As described above, parents are recruited to participation in the research after independently signing up to participate in Incredible Years, Parents as Teachers, or SafeCare, and the agency/site providing their parenting program would have already agreed to randomization (and experimental condition providers received their training in the SPSHK module). Following consent and before any intervention has occurred, the parents will be given a paper copy of the assessment. A member of the research team will distribute surveys (identified only by a unique code—see Section 9) at the beginning of the first session to parents who have consented to participate.

The assessment is given in a booklet format. At this assessment point, parent survey booklets include the APQ, AUDIT, CES-D, DAST, ISEL-SF, READI-SF, a demographics questionnaire, and the module assessment of parents’ attitudes, knowledge, and behaviors of CSA prevention (measures described above in Section 7.1). Providers in the group sessions (Incredible Years) will engage with parents who do not wish to participate separately at this time.

7.2.2 Parenting Intervention

Provide a description as defined above and format accordingly.

Participants complete 14 Incredible Years, 5 Parents as Teachers, or 6 SafeCare sessions, one per week for consecutive weeks. These are rough estimates of sessions as the number of sessions largely depends on parental mastery; that is, if a parent needs two sessions to get through a particular skill, the provider is trained to do that in their training of the parent-education model.

7.2.3 Post-parenting Intervention Assessment

Provide a description as defined above and format accordingly.

Completion of the parenting intervention is specific to each parenting program. For PAT, completion of intervention (for the purposes of our research) is at the end of the fifth foundational visit. For Incredible Years, completion of intervention (for the purposes of our research) is the penultimate session – this is the last session in which content is delivered; the final session is a celebration and graduation. For SafeCare, completion of intervention (for the purposes of our research) is at the conclusion of the parenting module (6 weeks).

Parents will be provided with another paper survey. Those who have not agreed to participate in the research will be allowed to leave. Participants will complete the APQ and Module Assessment (‘Measure_ParentAssessmentTool’ in supporting documents).

7.2.4 One-week Post-parenting (control) OR Post-parenting and Module Assessment (Experimental group)

Provide a description as defined above and format accordingly.

One-week after completing the parenting program (7.2.3), parents in the control condition that have agreed to participate in the research will be contacted by the research team to complete the third assessment, the APQ, Module Assessment ('Measure_ParentAssessmentTool'). {This will happen within a normally scheduled session of PAT or SafeCare, and will require an additional visit for the IY participants}

The week after the conclusion of event 7.2.3, providers in the experimental condition deliver the Smart Parents – Safe and Healthy Kids module to their parents. The parent and provider will complete a short survey about the content of the session. This is done each time the module is delivered to measure fidelity. Additionally, provider-participants will record any two SPSHK sessions where the participating parent(s) agree to the recording. If the parent in the individual session—or any parent in the group session—declines to be audio recorded, the SPSHK module will be delivered as usual (including the fidelity survey), but the session will not be audio recorded.

Immediately following delivery of the SPSHK module, those in the experimental group will complete the APQ, Module Assessment, and a questionnaire asking about their overall satisfaction with the module ('Measures_Parent Satisfaction Survey'). Parents will complete their fidelity assessment in addition to the Parent Satisfaction Survey ('SPSHK Parent Fidelity Monitoring') as part of their post-intervention assessment packet. As the parent fills out this form, the provider will complete the self-reported fidelity assessment ('SPSHK Provider Fidelity Monitoring_V2').

The audio recordings will be reviewed by the PSU study team using the 'SPSHK Research Fidelity Monitoring v2.1' form. The form assesses which aspects of the curriculum were delivered and to what degree (incomplete v. complete) to the family. These observations will be compared with provider self-report and parent report. Two visits will be recorded and scored for fidelity.

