1.3 Secondary Study Endpoints

State the secondary endpoints to be measured in the study.

The secondary endpoint to be measured in the study is the degree to which the CSA module (*Smart Parents – Safe and Healthy Kids*) is implemented with fidelity. We are assessing this in three ways: parent report, provider self-report, and observation through audio recording.

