3.2 Exclusion Criteria

List the criteria that define who will be excluded in your study.

1. Parent/caregiver does not speak English
2. Parent is mandated (i.e., court-ordered) to attend parent-training program

Providers who are not implementing SPSHK.

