3.3 Early Withdrawal of Subjects

3.3.1 Criteria for removal from study

Insert subject withdrawal criteria (e.g., safety reasons, failure of subject to adhere to protocol requirements, subject consent withdrawal, disease progression, etc.).

1. Participant decides to withdraw from the parent-training program
2. Participant decides to withdraw at any point from the survey

Providers who decide to not deliver the module.

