3.3.2 Follow-up for withdrawn subjects

Describe when and how to withdraw subjects from the study; the type and timing of the data to be collected for withdrawal of subjects; whether and how subjects are to be replaced; the follow-up for subjects withdrawn from investigational treatment.

If a participant (parent or provider) decides to stop before the study's conclusion, a member of the research team will ask if they wish to have their information used at all; if no, we will purge their information from our database. If the participant indicates that we can use their unidentifiable information, we will retain their available survey data and remove their identifiers from the master list.

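### Audio-observed fidelity is open to upward selection because providers choose which two sessions to record, and removing non-delivering providers hides non-delivery.

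*Combined protocol and SAP*

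**What the plan says.** Section 1.3 makes the secondary endpoint the degree to which the module is delivered as designed: "We are assessing this in three ways: parent report, provider self-report, and observation through audio recording".

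Providers at experimental sites are invited and consented when they are trained in the module, before they deliver it (sections 4.1, 4.2 and 5.1.1.1). Section 3.3.1 then lists among the criteria for removal: "Providers who decide to not deliver the module". Section 3.2 has a separate enrolment exclusion: "Providers who are not implementing SPSHK".

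On recording, section 7.1 says that, with the parent's permission, "the provider will audio record two experimental sessions". Section 7.2.4 leaves the choice open: "provider-participants will record any two SPSHK sessions where the participating parent(s) agree to the recording". The provider uploads the file and it is then deleted from the device (section 9.1.2). No log of sessions offered, declined or recorded is described.

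The parent and provider forms work differently. Of these short surveys section 7.2.4 says: "This is done each time the module is delivered to measure fidelity". They are completed even when a parent declines the recording. The study team scores the recordings and compares them with both reports (section 7.2.4). Section 2.1 gives the purpose: to learn whether one method would be enough, which would cut burden and cost in later work. Section 8.3 names no fidelity analysis set, no rule for non-delivery and no method of comparing the three measures.

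**The concern.** There are two separate issues.

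First, audio is the only fidelity measure not completed by a party to the session, so it is the natural reference for the other two. If providers may pick which sessions are heard, they can pick families or occasions they expect to go well. The recorded sessions would then look better than the provider's usual delivery. A conclusion that self-report or parent report is sufficient would rest on a favourable subset.

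Second, all three measures require a delivered session. A provider who enrols at training and then decides not to deliver leaves no fidelity data of any kind, and section 3.3.1 also takes that provider out of the study. The retention rule in section 3.3.2, under which "we will retain their available survey data and remove their identifiers from the master list", does not help, because there is no fidelity survey to retain. The reported result is then fidelity among delivered sessions. That is a legitimate quantity, but the plan does not say it is the target. Without a delivery count beside it, a reader facing a null trial result cannot easily tell an ineffective module from one that was not delivered.

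**Working it through.** **The plan's own figure.** Section 8.2 asks for two recordings from each of 100 providers, 2 × 100 = 200. It rests on unspecified other research, with no formula, precision or effect size, so it cannot be re-derived.

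**How much choice is there?** Planned module deliveries to enrolled experimental parents, from sections 8.1 and 8.2:
- Parents as Teachers, individual delivery: 62
- SafeCare, individual delivery: 62
- Incredible Years, group delivery: 14 groups
- Total: 62 + 62 + 14 = 138

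Per provider: 138 / 100 = 1.38. If each Incredible Years group has two co-leaders who each count the session (an assumption), it is (124 + 28) / 100 = 1.52. Either way the average is below two, and 138 deliveries cannot supply 200 separate session recordings.

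**Share of providers with a choice.** A choice exists only with three or more recordable sessions. If deliveries were spread over providers at random (Poisson, assumed), P(3 or more) is 0.16 at a mean of 1.38 and 0.20 at 1.52.

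**Worst-case shift for those providers.** Suppose the provider always records the two best of k sessions, with session scores normal within provider. The shift is the mean of the top two of k standard normal values:

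| k sessions | shift (within-provider SD) |
|---|---|
| 2 | 0 |
| 3 | 0.42 |
| 4 | 0.66 |
| 5 | 0.83 |

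These are upper bounds, because they assume perfect foresight or recording more than two sessions and keeping the best.

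**Average over providers.** Weighting the shifts by the Poisson(1.38) probabilities of 3, 4 and 5 sessions gives 0.110 × 0.42 + 0.038 × 0.66 + 0.0105 × 0.83 = 0.080; higher k brings it to about 0.083. The share with at least one delivery is 1 − 0.252 = 0.748. So the average worst-case shift is 0.083 / 0.748 = 0.11 within-provider SD per delivering provider.

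**Which measures are reached?**

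| | Session choice | Non-delivery |
|---|---|---|
| Audio | selected by provider | no data |
| Provider form | every delivery | no data |
| Parent form | every delivery | no data |

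**Non-delivery.** The documents give no rate. For illustration only, suppose delivered sessions score 90%. That figure is the same whether 5%, 10% or 20% of trained providers never deliver. The product of fidelity and uptake would be 0.90 × 0.95 = 0.855, 0.90 × 0.90 = 0.81 or 0.90 × 0.80 = 0.72. That product is a different quantity from fidelity. The gap shows what an unreported uptake figure conceals; it is not a bias in the 90%.

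**The case against.** A reader might infer that the fidelity endpoint as a whole is biased upward. The documents do not support that. Two of the three measures are taken at every delivery, so session choice cannot select them. Upward selection of the audio is a risk left open by the text, not something the text shows to occur.

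Nor does leaving out non-deliverers bias fidelity among delivered sessions. The researcher form in section 7.2.4 scores which parts of the curriculum were delivered and how completely, and a provider with no session has nothing to score. What is lost is uptake.

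Section 3.2 should not carry weight here. Since fidelity providers come only from experimental sites, its natural meaning is that control-condition providers are ineligible. Section 3.3.1 alone supports the removal point.

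The scope for choice is also small on the stated numbers, and because parents must agree to a recording, the choice will normally precede the session. This stands and limits the size. It does not close the matter. The plan wants 200 recordings and has 138 planned deliveries, so either more deliveries are expected or the target cannot be met. Whether sessions with parents who declined the surveys may be recorded is not stated, and deliveries may be concentrated in a few providers.

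Finally, the methods can be compared within recorded sessions, where all three reports exist, and missing forms would reveal non-delivery to the team. Both are true. But agreement in chosen sessions need not carry over to the rest, and the plan does not commit to reporting the delivery count.

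**Conclusion.** The point holds in a limited form. Audio-observed fidelity is at risk of upward selection because the provider chooses which consented sessions to record. Separately, removing enrolled providers who decide not to deliver means that the fidelity result covers delivered sessions only and hides non-delivery.

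The size is unknown. On the planned numbers about 80 to 84% of providers would have two or fewer sessions, and so no choice, if deliveries are spread at random. The 0.42 to 0.83 SD shifts are worst cases for providers with 3 to 5 sessions. The average worst case is about 0.11 SD per delivering provider, and it would be larger if deliveries are concentrated or if sessions with non-enrolled parents count. The change is worth making because it is cheap and concerns a named secondary endpoint and the planned comparison of methods. The primary outcome is not touched by session choice.

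**What to change.** - **Section 7.2.4:** replace the free choice with a fixed rule, such as the first two module sessions, in order of delivery, in which all parents present agree, both to be uploaded. 
- **Section 3.3.1:** keep a trained, consented provider who does not deliver in the provider count, recorded as a non-delivery.
- **Section 8.3:** define fidelity as a property of delivered sessions. Report beside it, not multiplied into it, the proportion of trained providers who delivered and of experimental parents who received the module. Compare the parent and provider form scores of recorded and unrecorded sessions, as a direct check on selection.
- **Section 8.2:** reconcile 200 recordings with 138 planned deliveries, and say whether sessions with non-enrolled parents may be recorded.

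The cost is protocol wording and a delivered yes/no count that should be readily available to the team. One small downside is that the first two sessions may be less practised than later ones, which could pull audio scores down a little. The comparison of recorded and unrecorded sessions would help to show this.
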